## **4. Sample size**

The partners in the proposal expect to recruit at least 80% of the eligible retreatment patients (those with RIF resistance -considered as MDR- and equal numbers of RIF sensitive patients) presenting for diagnosis and care. Based on previous years data, over 4700 patients at risk of RR TB are on average collectively being screened annually out of which 590 (15%) are diagnosed as being RR-TB (Table 2, in Background).

For the validation of the novel tests (Study 1), we will recruit all RR patients and equal numbers of RIF susceptible patients, for a total of 1420 RR- and 1420 RIF susceptible patients. In the table below, we summarize the power we expect to have to detect resistance to the key drugs:

**Table 3.** Sample size considerations against **phenotypic** gold standard (Phase 1), and the **genotypic** gold standard (Phase 2, see study flow chart in Annex 1), with each phase including 1420 patients, half of whom will have RR TB, for a total of 2840 patients.

Drug	Expected prevalence of resistance in RIF R (n=710 each phase)	Expected total prevalence of resistance (n=1420 each phase)	Expected sensitivity and precision against phenotypic test	Expected specificity and precision against phenotypic test	Expected sensitivity and precision against genotypic test	Expected specificity and precision against genotypic test
RIF	710 (100%)	710 (50%)	98% +/- 1%	98% +/-1%	98% +/- 1%	98% +/-1%
INH	675 (95%)	923 (65%)	90% +/- 1%	98% +/-1%	98 +/- 1%	98% +/-1%
FQ	43 (6%)	43 (3%)	85% +/- 8%	98% +/-1%	98%, range 88%-100%	98% +/-1%

RIF= rifampicin, INH=isoniazid, FQ=fluoroquinolones

The estimated prevalence of resistance is based on the WHO report (1) and personal communications. This sample size will be ample to validate these tests for resistance to RIF, isoniazid, and fluoroquinolones, according to established guidelines (9).

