### 1. Study design:

Two multi center observational studies will be conducted:

- *Study 1:* Cross sectional study for TB cases aged  $\geq 15$  (all RIF resistant (RR) ones (new cases or retreatment patients) and equal number of RIF sensitive retreatment

patients from the same country) with comparison of TB resistance diagnostic test performance at baseline. There are 2 phases in this project; phase 1 is the comparison of Deeplex results against the phenotypic results (Gold standard), phase 2 is the comparison of Insilixa and Xpert 2nd generation results against Deeplex (gold standard).

- *Study 2:* Cohort study of RR-TB patients (recruited in Study 1) under treatment with comparison of the performance of FDA or Xpert compared to solid culture

The study flow chart is placed in annex 1 of this protocol

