## 6. Data management & Data Collection

### **Data collected:**

For each patient enrolled in study 1 & 2, an expanded laboratory request form will be completed.

For all patients the following data will be collected:

- Baseline characteristics (mostly those collected from routine monitoring, including demographic- and contact information, detailed treatment history including details such as failure vs relapse prior MDR treatment, return after loss to follow-up), risk factors for (resistant) TB
- Phenotypic drug sensitivity tests (phase I of Study 1 only)
- Deeplex results (phase I and II of the Study 1)
- Programmatic treatment outcomes

In addition:

- for the phase 2 of the study 1 (validation of InSilixa and 2nd line Xpert test) the results of these 2 tests (InSilixa and 2nd line Xpert) will also be recorded
- for all patients enrolled as RR, the following additional information will be recorded:
  - monthly FDA results,
  - monthly GeneXpert and culture results,
  - treatment outcomes

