## **9. Data Analysis**

For the phase I and II of the study 1 (validation of Deeplex against phenotypic DST & validation of InSilixa and Xpert 2nd generation against Deeplex results), we will validate the molecular assays for their performance (Se and Sp) on the diagnosis of RIF resistance, against phenotypic DST on solid medium as gold standard, with resolution of discordances by classic target sequencing of the *rpoB* gene. Similar analyses will be conducted to determine the performance for the diagnosis of isoniazid and fluoroquinolone resistance.

An interim analysis will be performed after 350 RR-TB patients have been recruited in order to test our assumptions regarding resistance proportions and consider adjustment of sample size or recruitment strategy.

For the study 2, the results will be analyzed with time dependent Cox regression to identify the optimal time point to identify patients who are at risk of failing treatment.

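### Table 3 uses one resistance count per drug for both phases, although the reference changes from phenotypic DST to Deeplex. On its own figures Phase 2 would have about 64 fluoroquinolone reference-positives, not 43, about 43% of them phenotypically susceptible.

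*Combined protocol and SAP*

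**What the plan says.** Methods section 4 plans two phases of equal size, "with each phase including 1420 patients, half of whom will have RR TB, for a total of 2840 patients". Table 3 then lists one count per drug under "Expected total prevalence of resistance (n=1420 each phase"): RIF 710, isoniazid (INH) 923, FQ 43. All 43 FQ-resistant patients also appear in the RR column (43 of 710). The count columns name no reference standard. Their stated source is the WHO report and personal communications.

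The FQ row expects 85% +/- 8% sensitivity and 98% +/- 1% specificity against the phenotypic test. For sensitivity against the genotypic test it prints "98%, range 88%-100" (per cent).

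Methods section 1 describes the second phase as follows: "phase 2 is the comparison of Insilixa and Xpert 2 nd generation results against Deeplex (gold standard"). The data-collection list in section 6 includes "Phenotypic drug sensitivity tests (phase I of Study 1 only"). The background section on Xpert 2nd line restricts that cartridge to patients who test RR.

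**The concern.** A count of resistant patients is the denominator for sensitivity, and it depends on which test defines resistance. Table 3 itself expects Deeplex and phenotypic DST to disagree, so one count cannot be right under both standards. With FQ resistance at only 3%, a 2% false-positive rate among the other 97% adds almost as many reference-positives as there are true ones.

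The Phase 2 FQ result is meant to validate InSilixa and Xpert 2nd line, and the plan calls the sample size ample for this. If a large share of the Phase 2 reference-positives are phenotypically susceptible, agreement with Deeplex and detection of phenotypic resistance are different quantities. The Phase 2 data alone cannot separate them.

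**Working it through.** **Inputs (all from Table 3).** N = 1420 per phase, 710 of them RR. Counts R: RIF 710, INH 923, FQ 43. Against phenotype: RIF 98%/98%, INH 90%/98%, FQ 85%/98% (sensitivity/specificity). The confidence level is not stated; I assume 95% two-sided.

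**1. The plan's own figure.** 42/43 = 97.7%, exact (Clopper-Pearson) 95% interval 87.7% to 99.9%. This is the printed 88% to 100%, so the Phase 2 FQ range was computed on 43.

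**2. Deeplex-positives if the counts are phenotypic.** Expected positives = Se x R + (1 - Sp) x (N - R).

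- FQ: 0.85 x 43 + 0.02 x 1377 = 36.55 + 27.54 = 64.1. Phenotypically susceptible share: 27.54/64.09 = 43%.
- FQ, RR only: 36.55 + 0.02 x 667 = 36.55 + 13.34 = 49.9. Share: 13.34/49.89 = 27%.
- FQ, RIF-susceptible only: 0.02 x 710 = 14.2, all phenotypically susceptible.
- INH: 0.90 x 923 + 0.02 x 497 = 830.7 + 9.9 = 841, against 923 printed.
- RIF: 0.98 x 710 + 0.02 x 710 = 710, unchanged.

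**3. Range over the printed margins.**

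| | Inputs varied | Count | Phenotypically susceptible |
|---|---|---|---|
| FQ, all | Se 77-93%, Sp 97-99% | 47 to 81 | 26% to 56% |
| FQ, RR only | Se 77-93%, Sp 97-99% | 40 to 60 | 14% to 38% |
| INH | Se 89-91%, Sp 97-99% | 826 to 855 | not needed |

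In the full 1420 the FQ count never falls to 43. At Se 85% that needs Sp = 1 - (43 - 36.55)/1377 = 99.5%. In RR patients alone, 43 lies inside the range.

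**4. The other reading, with 43 as the Deeplex count.** Solving 0.85R + 0.02(1420 - R) = 43 gives R = (43 - 28.4)/0.83 = 17.6, about 18 phenotypically resistant patients in Phase 1. The 95% Wald half-width at 85% is then 1.96 x sqrt(0.85 x 0.15/17.6) = 17 points, against the printed 8. One phase is misdescribed on either reading.

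**5. Effect on precision (exact 95%).**

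- 63/64: 91.6% to 100%.
- 49/50: 89.4% to 99.9%.
- 39/40, the bottom of the RR-only range: 86.8% to 99.9%, about one point wider than printed.
- INH sensitivity at 98%: half-width 0.90 points on 923 and 0.95 on 841, both +/-1 after rounding.

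**6. What 98% requires.** Suppose the new test detects every phenotypically resistant Deeplex-positive (TP). To reach 98% overall it must repeat a share 0.98 - 0.02 x TP/FP of the phenotypically susceptible ones (FP). For FQ this is 0.98 - 0.02 x 36.55/27.54 = 95%, or 26.3 of 27.5 calls. Over the printed margins it is 92% to 96%.

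At the other extreme, errors are independent given phenotype. With 98% detection of TP and 2% of FP, agreement is (0.98 x 36.55 + 0.02 x 27.54)/64.09 = 57%. In RR only it is (0.98 x 36.55 + 0.02 x 13.34)/49.89 = 72%.

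**The case against.** A reader might infer that the printed FQ range is an arithmetic error, or that Phase 2 is too small. Neither is supported. The range reproduces from 42/43, and at 64 or 50 reference-positives the interval is narrower. The 98% is an assumed agreement with Deeplex, so a different count cannot refute it.

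A reader might also take 57% as the expected Phase 2 FQ sensitivity. It is a lower bound that needs independent errors between molecular tests aimed at resistance mutations, which is implausible as a central case. Full repetition is not assured either: the background describes InSilixa as reading 117 fixed mutations, while Deeplex sequences whole targets.

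Nor do the documents show that Deeplex-only calls are mistakes. The synopsis says few laboratories perform phenotypic DST correctly, and the study sets out to examine heteroresistance. The Data Analysis section plans comparison "with resolution of discordances by classic target sequencing of the" rpoB gene for RIF, with similar analyses for INH and FQ. Sequencing could, however, confirm a mutation in a phenotypically susceptible patient, so it need not remove these calls. Table 3 does not say whether its 98% is before or after resolution.

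The 64 also depends on reading a rounded 98% specificity literally across 1377 patients. That stands, and is why a range belongs with it. The interim analysis after 350 RR patients will check resistance proportions, but the plan does not say it will compare Deeplex with phenotype.

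Finally, if Deeplex is the reference, the roughly 14 RIF-susceptible positives do inform agreement with Deeplex. Dropping them is not required.

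**Conclusion.** The concern holds in a limited form. Table 3 cannot use one count for two reference standards that it expects to differ. If the counts are phenotypic, Phase 2 has about 64 FQ reference-positives (47 to 81), about 43% of them phenotypically susceptible (26% to 56%). In RR patients the figures are about 50 (40 to 60) and 27% (14% to 38%). INH is about 841 instead of 923, and RIF is unchanged.

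At the central counts the printed FQ range is conservative, and INH and RIF precision are unchanged after rounding. The real consequence is interpretive. An FQ agreement near 98% would show that the new tests repeat Deeplex, including most calls that phenotypic DST would not support. With phenotypic DST confined to Phase 1, the Phase 2 data cannot show how much of the agreement this is.

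These sizes assume that the counts are phenotypic, that the table's sensitivity and specificity apply uniformly across RIF strata, and that no calls are reclassified after sequencing.

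**What to change.** 1. State in Table 3 which reference defines each count. Add Phase 2 counts of Deeplex-positives and Deeplex-negatives with ranges: FQ about 64/1356 (positives 47 to 81), INH about 841/579 (positives 826 to 855). Restate the Phase 2 FQ interval on these counts. For Xpert 2nd line use the RR-only FQ counts, about 50/660 (positives 40 to 60), because the background limits that cartridge to RR patients.
2. From Phase 1 data, tabulate by RIF stratum the share of Deeplex FQ-positives that are phenotypically resistant. Print it beside the Phase 2 FQ result, and label that result as agreement with Deeplex.
3. Report Phase 2 FQ results by RIF stratum.

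The cost is table and wording changes plus one tabulation of data already planned. Making RR the main FQ analysis for InSilixa is optional. It would cut the Deeplex-negatives from about 1356 to 660 and widen the specificity half-width at 98% from about 0.7 to 1.1 points.

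### Table 3 understates the uncertainty of two phenotypic sensitivities: fluoroquinolone 85% on 43 resistant patients is about ±11 points at 95% (8 printed); isoniazid 90% on 923 is about ±2 (1 printed, minor)

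*Combined protocol and SAP*

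**What the plan says.** Table 3 (Methods, section 4) is built on per-phase counts. Its caption describes the plan as "with each phase including 1420 patients, half of whom will have RR TB, for a total of 2840 patients", and it ties the phenotypic reference to phase 1 and the genotypic reference to phase 2. The expected numbers of resistant patients per phase are 710 for rifampicin (RIF), 923 for INH and 43 for FQ.

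Under the header "Expected sensitivity and precision against phenotypic test" the table prints 98% ± 1% for RIF, 90% ± 1% for INH and 85% ± 8% for FQ. Against the genotypic reference, the FQ sensitivity cell reads "98%, range 88%-100" (per cent). The table gives no confidence level and no formula. The text below it concludes: "This sample size will be ample to validate these tests for resistance to RIF, isoniazid, and fluoroquinolones, according to established guidelines (9".

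Three other places bear on which patients have a phenotypic result:

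- Study design (section 1): "phase 1 is the comparison of Deeplex results against the phenotypic results (Gold standard".
- Data collected (section 6): "Phenotypic drug sensitivity tests (phase I of Study 1 only".
- Data Analysis (section 9): the sentence opens "For the phase I and II of the study 1 (validation of Deeplex against phenotypic DST", and its bracket goes on to name Deeplex as the comparator for the two simpler tests. Its main clause then says that RIF performance of the molecular assays will be assessed "against phenotypic DST on solid medium as gold standard", without limiting this to phase 1.

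**The concern.** The precision of a sensitivity depends on the number of truly resistant patients. For FQ that is 43 per phase, the smallest denominator in the table. A half-width of 8 points around 85% looks too tight for 43 patients, and 1 point around 90% looks too tight for 923.

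Validating Deeplex is a primary objective, and FQ sensitivity is by far its least precise planned estimate. The statement that the sample is ample for FQ can be judged only from these cells. The guideline it invokes is cited as reference 9, which in the reference list is the InSilixa company web page, so the protocol contains no precision criterion to compare with. If the FQ cell is too narrow, readers will expect a firmer lower bound than the design can give. The interim look after 350 rifampicin-resistant (RR) patients would also start from an understated half-width.

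**Working it through.** **Inputs (Table 3, per phase).** Resistant: RIF 710, INH 923, FQ 43, of 1420. Non-resistant, by subtraction: RIF 1420 − 710 = 710; INH 1420 − 923 = 497; FQ 1420 − 43 = 1377. The confidence level is not stated; two-sided 95% (z = 1.96) is assumed and tested in step 3.

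**Formula.** Half-width = z × √(p(1 − p)/n).

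**Step 1. Cells that reproduce at 95%.**

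| Cell | p | n | Half-width (points) | Printed |
|---|---|---|---|---|
| RIF sensitivity and specificity | 0.98 | 710 | 1.03 | 1 |
| INH sensitivity, genotypic | 0.98 | 923 | 0.90 | 1 |
| INH specificity | 0.98 | 497 | 1.23 | 1 |
| FQ specificity | 0.98 | 1377 | 0.74 | 1 |

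The FQ genotypic sensitivity also reproduces: the exact 95% interval for 42/43 is 87.7% to 99.9%, printed as 88% to 100%.

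**Step 2. The two cells that do not.**

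- FQ, phenotypic: 1.96 × √(0.85 × 0.15/43) = 1.96 × 0.0545 = 10.7 points, against 8 printed. Wilson gives 10.6 and Agresti-Coull 11.0.
- INH, phenotypic: 1.96 × √(0.90 × 0.10/923) = 1.96 × 0.00987 = 1.9 points, against 1 printed. Wilson and Agresti-Coull also give 1.9. Using only the 675 INH-resistant patients among RR cases gives 2.3, which is further away.

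**Step 3. Could another confidence level explain them?**

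| Level | FQ 85%, n = 43 | INH 90%, n = 923 | Exact lower limit, 42/43 |
|---|---|---|---|
| 95% | 10.7 | 1.9 | 87.7% |
| 90% | 9.0 | 1.6 | 89.4% |
| 85% | 7.8 | 1.4 | 90.5% |
| Printed | 8 | 1 | 88% |

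At 90% neither ± cell is reached. At 85% both round to the printed values, but the level is unusual and misses the 88% limit in the same FQ row. A half-width of exactly 8 at n = 43 corresponds to about 86% confidence.

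**Step 4. Could another denominator explain them?** With both phases pooled, at 95%: FQ n = 86 gives 7.5 and INH n = 1846 gives 1.4. Both round to the printed values.

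**Step 5. Size of the FQ discrepancy.**

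- Printed: 85 ± 8, that is 77% to 93%.
- Same type of interval at n = 43: 74.3% to 95.7%.
- Exact intervals: 69.3% to 93.2% for 36/43 (83.7%) and 72.1% to 94.7% for 37/43 (86.0%). No whole count gives 85%, since 0.85 × 43 = 36.55.
- Resistant patients needed for ±8 at 95%: (1.96/0.08)² × 0.1275 = 76.5, so 77 against the 43 expected.

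**The case against.** The strongest reply is that the cells were calculated correctly and only the label is wrong. Deeplex is run in both phases. If the phenotypic columns used both phases and the genotypic columns used phase 2 alone, every cell fits at 95%. The phenotypic half-widths become RIF 0.73 (n = 1420), INH sensitivity 1.37 (n = 1846), INH specificity 0.87 (n = 994), FQ sensitivity 7.55 (n = 86) and FQ specificity 0.52 (n = 2754). The main clause of the Data Analysis sentence can be read that way, and the laboratory section describes culture and first-line susceptibility testing as routine everywhere.

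As an account of how the numbers arose, this is plausible. It does not rescue them. The table's headers are per phase, its caption links the phenotypic reference to phase 1, the study design does the same, and the data collection list restricts phenotypic results to phase 1. Under those statements 86 FQ-resistant patients with a phenotypic result will not exist.

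A second reply is that 95% is only an assumption. That is true. The ±1% cells do not settle it, because they also round to 1 at 85% and 90%. The support comes from the one cell printed as a range, which may have been calculated by a different method.

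A third reply is that little turns on the error: no decision rule uses these cells, the like-for-like lower limit moves only from 77% to 74%, and the interim look can revisit sample size. This rightly limits the weight of the point. The 69% limit, in particular, comes from a count below the planned 85% and a change of interval type. But the interim look tests resistance proportions; it does not correct a printed precision.

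**Conclusion.** The point holds. Given a 95% level and phenotypic testing in phase 1 only, Table 3 understates the FQ half-width by about 2.7 points (10.7 against 8) and the INH half-width by about 0.9 (1.9 against 1). The INH error is minor. The FQ error matters more because it flatters the weakest estimate under a primary objective: the lower limit is about 74% on the table's own type of interval, or 69% to 72% on exact intervals, not 77%.

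The 95% level is inferred, mainly from the FQ genotypic range. The phase restriction is stated in the study design and the data collection list and follows from the table caption; the Data Analysis wording is not reconciled with them. Pooling of the two phases is a likely origin of the two cells, but the protocol does not say so. None of this shows that ±11 points fails a requirement, because the protocol gives none.

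**What to change.** 1. State the 95% confidence level and the interval method in Table 3.
2. Restate two cells from the phase 1 counts, using one type of interval: FQ sensitivity 85% ± 11% and INH sensitivity 90% ± 2%.
3. Make the statement that the sample is ample refer, for FQ, to the corrected precision.
4. Align the Data Analysis section with the Table 3 caption, the study design and the data collection list on which phase uses phenotypic testing as the reference. If the sponsor did intend phenotypic testing in both phases, those three places and the table headers would have to change instead.

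The cost is two table cells, one stated level and some wording. The stated FQ precision becomes less favourable. No added enrolment and no change of analysis is proposed.

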## Synopsis

The proposed DIAMA (DIagnostics for Multidrug resistant tuberculosis in Africa) study aims to address current gaps in the diagnosis and management of patients with Multi-Drug-Resistant (MDR) tuberculosis (TB). Building on existing networks and research collaborations, the project aims to evaluate and implement rapid and accurate molecular tests for resistance to anti-TB drugs, to replace the current dependency on phenotypic drug resistance testing (DST), which takes up to 4 months and is technically so demanding that few laboratories can perform these tests correctly.

The project builds on the World Health Organization (WHO) recommended continuous surveillance of patients for rifampicin resistance. Two African partners with advanced molecular laboratories will establish reference laboratories for the 'Deeplex' assay, a novel multiplex deep sequencing-based drug resistance diagnostic platform that simultaneously provides sequence information of genes that confer resistance to key TB drugs. Partners will recruit all patients with RR TB, and a subset of those with rifampicin sensitive TB. In a first phase, sputum will be shipped for the Deeplex assay, for comparison against phenotypic DST to 1st and 2nd line drugs. In a second phase, InSilixa and Cepheid 2nd line Xpert, two 'lower tech' tests at the last stages of laboratory validations, will be implemented in all countries that have established recruitment of retreatment patients. The InSilixa lab-on-chip assay, powered by a smartphone, is able to query 117 drug resistance conferring mutations at around \$20 per test. The Cepheid Xpert 2nd line cartridge can be implemented in existing Xpert machines used for the Xpert MTB/Rif assays. These two tests will be compared versus the Deeplex assay.

Using the latest advances in e-Health software 'DataToCare', molecular results would be communicated in real time to the National TB Programs, so that MDR patients can swiftly start appropriate treatment.

Lastly, once patients have initiated MDR treatment, they will be monitored for treatment success by faster alternative approaches to the WHO recommended monthly cultures: serial sputum samples will have Fluorescein DiAcetate (FDA) vital stain microscopy and measurement of the bacterial load using the Xpert MTB/Rif.

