## **2. Rationale**

We anticipate that the impact of the DIAMA project, if the results are as promising as expected, will be potentially paradigm-shifting. We foresee that MDR-TB will move from an often terminal illness with grave prognosis to a readily recognizable and treatable disease, in which treatment success can be predicted early, so treatment can be modified in 'real' time. The novel tests that identify specific resistance to particular drugs used for the treatment of resistant TB allow for a way of 'personalized medicine', and by monitoring the impact of specific mutations on the outcome of MDR treatment, we anticipate learning which mutations should lead to treatment modifications in order to enhance the chance of treatment success. In addition, we will learn whether heteroresistance, which is the simultaneous occurrence of bacterial populations with and without resistance, is of clinical relevance. Lastly, the fact that the Deeplex assay gives full sequence information on a large number of genes allows us to detect, for the first time, whether different mutations are common in circulating drug resistant strains in the participating countries in Sub-Saharan Africa. Such results will thus not only inform the treatment algorithms used in clinical trials for MDR-TB, yet also provide fundamental insights into the pathogenesis underlying the development of TB resistance.

Once the validation of the novel diagnostic tests for TB resistance mutations will be completed in the DIAMA proposal, the companies that have developed these tests will

include these results in their respective applications for approval by regulatory authorities, and for endorsement by WHO. The monitoring of MDR patients on treatment with FDA microscopy is readily implementable in most peripheral microscopy centers.

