## **2. Study settings**

The study takes place in nine African countries (Benin, Cameroon, DRC, Ethiopia, Guinea, Mali, Nigeria, Rwanda and Senegal) with patients recruited at a national or regional level (depending on country size), and the samples tested in the respective reference laboratory (see partners). All partners involved in this study have or will implement(ed) a routine system of screening all TB patients at risk for resistant TB aged  $\geq 15$  with Xpert/MTbRif.

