### **Specific tests**

In all settings, smear microscopy with Ziehl-Neelsen (ZN) or auramine/rhodamine (A/R), culture, 1st line drug susceptibility testing (DST) and Xpert MTB/Rif are routinely used. Where 2nd line DST on solid culture is not yet available, the project will help implementing the recommended tests on a routine basis. If implementation is not possible in a reasonable framework, respective samples will be tested in one of the study reference labs (LRM Cotonou, RBC Kigali or ITM Antwerp), together with the Deeplex.

Samples will undergo direct auramine microscopy and direct FDA microscopy. All samples (including AFB negative) will undergo Xpert MTB/Rif testing and culture.

As all partners already conduct phenotypic DST, the culture and first-line phenotypic DST will be conducted on-site, following training for second line DST by the Lowenstein Jensen proportion method as necessary. Participating laboratories will receive periodic External Quality Assessment (EQA) panels from the ITM in Antwerp. Surplus sputum will be stored at

-20C and serves for testing additional bacterial diagnostic tests, such as the InSilixa and Cepheid 2nd line tests available in the second phase of study 1.

Partners are moreover encouraged to follow WHO guidelines regarding the use of Line Probe Assays (LPA) for FQ and injectable resistance for RR patients, which is not part of the DIAMA study protocol. Given the intrinsic delays of shipments in phase I, and the fact that the Deeplex is not yet validated in phase I, the use of such LPAs will support the appropriate choice of treatment regimen for RR patients. The partner laboratories will however be able to request results from Deeplex testing to weigh these 'unvalidated' results in the choice of a salvage regimen in case patients fail their RR treatment.

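### Table 3's +/-1% precision makes no allowance for differences between the nine countries or their DST laboratories, and the analysis plan has no step that would reveal them

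*Combined protocol and SAP*

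**What the plan says.** Methods 4 (Sample size) introduces Table 3 with the words "we summarize the power we expect to have to detect resistance to the key drugs". The table is laid out "with each phase including 1420 patients, half of whom will have RR TB, for a total of 2840 patients". Each drug has one expected sensitivity and one expected specificity against the phenotypic reference (phase 1) and against the genotypic reference (phase 2), with a +/- figure or a range. No confidence level, interval method or allowance for country is given. The section concludes: "This sample size will be ample to validate these tests for resistance to RIF, isoniazid, and fluoroquinolones".

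On where the data arise, Methods 2 (Study settings) says "The study takes place in nine African countries", with "the samples tested in the respective reference laboratory". Methods 8 (Specific tests) adds that "the culture and first-line phenotypic DST will be conducted on-site". Second-line DST is done locally after training where possible, and otherwise in one of the study reference laboratories.

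Methods 9 (Data Analysis) plans sensitivity and specificity for RIF, with discordances resolved by *rpoB* sequencing, and similar analyses for INH and FQ. It mentions no country or laboratory stratum, no random effect and no check for heterogeneity. The interim analysis looks only at resistance proportions.

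**The concern.** A single-sample binomial half-width is the right measure of uncertainty for a wider population only if accuracy is the same everywhere. The protocol gives reasons to check that. The Synopsis says of phenotypic DST, the phase 1 reference standard, that it "is technically so demanding that few laboratories can perform these tests correctly". The Rationale treats it as an open question "whether different mutations are common in circulating drug resistant strains in the participating countries in Sub-Saharan Africa". A weaker reference laboratory, or mutations that the assay covers less well, would lower measured accuracy in one country and not in another.

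Two things are at stake. First, the Background speaks of benefit to whole regions, and the Rationale of regulatory applications and WHO endorsement. For such use, an interval that ignores country claims more precision than the design gives. Second, a problem in one laboratory can stay hidden in the pooled figure, because no planned analysis looks for it.

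**Working it through.** **Inputs.** From Table 3: RIF 98%, 710 resistant and 710 susceptible per phase; INH sensitivity 90% (phenotypic) and 98% (genotypic), 923 resistant, so 1420 - 923 = 497 susceptible; FQ sensitivity 85% (phenotypic), 43 resistant, so 1420 - 43 = 1377 susceptible; specificity 98% throughout. From Table 2: yearly RR-TB diagnoses of 30, 80, 150, 55, 100, 20, 55, 90 and 10, total 590. Assumed: 95% two-sided intervals, recruitment in proportion to Table 2, and the between-country SD, for which the documents give no value.

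**Step 1: reproduce Table 3.** Half-width = 1.96 x sqrt(p(1-p)/n).

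- RIF sensitivity and specificity: 1.96 x sqrt(0.98 x 0.02/710) = 1.03 points (printed 1).
- INH sensitivity, genotypic: n=923, 0.90 (printed 1).
- INH specificity: n=497, 1.23 (printed 1).
- FQ specificity: n=1377, 0.74 (printed 1).
- INH sensitivity, phenotypic: 1.96 x sqrt(0.90 x 0.10/923) = 1.94 (printed 1). The printed figure matches one standard error (0.99). A 95% half-width of 1 point would need 1.96^2 x 0.09/0.01^2, or about 3458 INH-resistant patients.
- FQ sensitivity, phenotypic: 1.96 x sqrt(0.85 x 0.15/43) = 10.7 (printed 8).

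So nine of the ten +/-1% cells are single-sample binomial figures after rounding. The INH cell and the FQ sensitivity cell do not reproduce even without a country effect.

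**Step 2: effective number of countries.** With w the country shares, sum(w^2) = 54450/590^2 = 54450/348100 = 0.156, and 1/0.156 = 6.4. The uneven recruitment behaves like about 6.4 equal countries.

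**Step 3: add between-country variation.** If the nine countries stand for a wider population, variance = p(1-p)/n + 0.1564 x SD^2. The 95% half-widths in points are:

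| Cell | SD 0 | SD 0.5 | SD 1 | SD 2 |
|---|---|---|---|---|
| RIF Se or Sp, n=710 | 1.03 | 1.10 | 1.29 | 1.86 |
| INH Sp, n=497 | 1.23 | 1.29 | 1.45 | 1.98 |
| FQ Sp, n=1377 | 0.74 | 0.83 | 1.07 | 1.72 |
| INH Se genotypic, n=923 | 0.90 | 0.98 | 1.19 | 1.79 |
| INH Se phenotypic, n=923 | 1.94 | 1.97 | 2.08 | 2.48 |
| FQ Se phenotypic, n=43 | 10.67 | 10.68 | 10.70 | 10.78 |

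RIF reaches 1.5 points, and so stops rounding to 1, at SD = sqrt(((0.015/1.96)^2 - 0.0196/710)/0.1564) = 1.4 points. At that SD the country part alone is 1.96 x sqrt(0.1564) x 1.4 = 1.1 points, so more patients from the same nine countries could not bring the figure back to 1.0.

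**Step 4: the nine countries as fixed.** The true variance of the pooled estimate is then sum(w p_j(1-p_j))/n, where p_j is accuracy in country j. This equals (pbar(1-pbar) - V)/n, where pbar is the weighted mean and V the weighted variance of the p_j. It is never larger than the pooled binomial variance, so for this target country differences do not make the interval too narrow.

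**Step 5: masking, which needs no assumed SD.** Take a country with Benin's share, 30/590 = 5.1%, purely as an example. If its sensitivity were 18 points below the rest, the pooled figure would move by 0.051 x 18 = 0.9 points, inside the stated +/-1.

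**The case against.** The strongest reply is that the widening depends on a target the protocol never defines. The sites are an existing partner network, not a sample of countries, and for their own average the pooled interval is adequate (step 4). That stands, so the widening is conditional on wider use.

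A reader might infer that the planned 95% interval would cover only 88% or 72% of the time at an SD of 1 or 2 points. The formula gives those values, but the documents do not support them as a finding: they specify no interval, do not define the target, and give no between-country SD. An SD of 2 points around 98% is already large, since a normal spread would put 16% of countries above 100%.

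A reader might also infer that even slight variation breaks Table 3. It does not at the printed rounding: up to an SD of about 1.4 points, RIF still prints as +/-1%. Nor is 1420 the denominator of any cell.

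The DST-laboratory argument reaches only the phenotypic columns. In phase 2 the reference is Deeplex, run in two African laboratories with ITM as back-up. Variation there would have to come from circulating mutations or from how the new tests are run in each country. The Synopsis remark on DST is general and not about these laboratories, and the Rationale asks a question about mutations and predicts nothing. External quality panels, second-line DST training, and *rpoB* sequencing of RIF discordances should all reduce laboratory differences. These points limit the likely size of the effect, but no planned analysis checks whether the measures worked.

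Finally, the data are thin for modelling. At 98% sensitivity, 710 patients give about 14 RIF errors in all: about 0.2 in Senegal, 0.5 in Mali and 0.7 in Benin. Senegal would have about 12 RR patients, and 12 of 12 correct has an exact interval of 74% to 100%. This rules out a random-intercept model as the only primary interval, but not descriptive reporting by country.

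**Conclusion.** The point holds in a limited form. Table 3 assumes no between-country variation without saying so, and the analysis plan would neither detect nor allow for it. For use beyond these nine countries, the RIF half-width rises from 1.03 to about 1.1, 1.3 or 1.9 points at SDs of 0.5, 1 or 2. Those SDs are assumptions, as are the 95% level and recruitment in proportion to Table 2. For the nine countries as fixed, the pooled interval is adequate and only the masking problem remains.

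This does not overturn the claim that the sample is ample. Its weakest support is FQ sensitivity, where 43 cases give about +/-10.7 points against a printed 8, and country variation adds almost nothing. The phenotypic INH sensitivity cell is wrong for a separate reason: about +/-1.9 against a printed 1 before any country effect. The change is worth making because it uses data already collected.

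**What to change.** In Methods 9:

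- Pre-specify sensitivity and specificity by country (by DST laboratory in phase 1) with exact intervals, to be read descriptively because small countries contribute few cases.
- Add, as a sensitivity analysis, a pooled interval that allows for country: cluster-robust or random-effects, with a small-sample correction for nine clusters.
- State whether the target is these nine countries or a wider population.

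In Table 3:

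- State the confidence level and interval method.
- Correct the phenotypic sensitivity cells for INH and FQ, or explain how they were obtained.
- Say that the precision assumes no between-country variation, and show the range in the table above.

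The cost is wording and a restated table, with no added patients, visits or samples. The downsides are a somewhat wider pooled interval in the sensitivity analysis and imprecise estimates for small countries. With Table 2 shares, the 43 FQ-resistant cases would be spread at about 1 to 11 per country.
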